9. PRIMARY OBJECTIVE: SAFETY EVALUATION (SS)

9.1. Extent of Exposure

IP exposure will be characterized by the number of IP administrations received (1 or 2) and N (%) of subjects reported as receiving a complete dose as recorded on the eCRF. Summary statistics will be provided for change in delivery device weights to reflect amount of IP delivered. IP exposure tables will display results by the 5 treatment groups and will be repeated for the SS and the EVAL sets.

9.2. Adverse Events (AEs)

Adverse events were to be recorded from informed consent through Day 57 + 28 days. For subjects receiving only one IP administration, follow-up was 28 days. Serious adverse events were recorded through Day 209. During the study treatment period (through Day 57) subjects were asked non-leading questions to determine the occurrence of spontaneously reported (unsolicited) AEs.

Symptoms were collected for the 7 days following each IP administration using Symptom Memory Aids (SMA), with clinical interpretation by the site investigators. A symptom recorded by the subject on the Symptom Memory Aid (SMA) may or may not have been reported as a solicited AE. For clinical interpretation Investigators used the, "Instructions to site investigators on assessing AEs from symptom memory aids (16 October 2019)" as a guideline in assessing whether a symptom was to be reported as an AE. The investigator was responsible for determining the severity and the relationship to IP for these SMA-based (solicited) AEs. There was no reconciliation of the database between the SMA symptoms and adverse event reports.

Symptom Memory Aids were used to facilitate assessment of AEs, as described in Protocol Section 6.2.1.6. Events that were reported in the Symptom Memory Aid were reviewed by the study staff and assessed and recorded as AEs. Investigators were instructed to clinically assess, and record individual symptoms reported by subjects as AEs in order to ensure that all reactogenicity events were captured. However, Protocol Section 9.6 states "Whenever possible, diagnoses should be given when signs and symptoms are due to a common etiology (e.g., cough, runny nose, sneezing, sore throat, and head congestion should be reported as "upper respiratory infection"). After medical review of the AE listing, it appears that some AEs should be grouped as diagnoses. For example, a subject who reported concurrent cough, runny nose, and sneezing assessed by the investigator as unrelated to vaccine should have those symptoms grouped as a syndromic diagnosis (URI), with the severity based on the most severe

AE/symptom. Therefore, as a secondary presentation, subjects with 3 or more concurrent unrelated AEs of cough, runny nose/rhinorrhea, sneezing, sore throat, itchy throat, itchy eyes, congestion, nasal irritation, hoarseness, headache, body aches/myalgia, tiredness/fatigue, malaise, and fever will have those AEs grouped as URI. This will simplify presentation of the data and is consistent with the protocol.

To facilitate the above reporting standard a total of 15 different AE Preferred Terms (Arthralgia, Cough, Fatigue, Headache, Malaise, Myalgia, Nasal congestion, Nasal discomfort, Nasopharyngitis, Oropharyngeal pain, Paranasal sinus discomfort, Pyrexia, Rhinorrhea, Sinus congestion, or Throat irritation) were considered for contribution to a syndromic diagnosis of URI. Subjects who reported symptoms that resulted in coding of 3 or more of these PTs on a given day, assessed by the Investigator as unrelated to the vaccine, were reported as URI. The severity of the URI was reported as the worst severity of the qualifying AEs considering only days when 3 or more terms were reported. AEs already reported by the Investigator as a URTI were not included in the URI data display.

Targeted physical examinations were conducted throughout the study. PE findings recorded as clinically significant, severe, or life threatening were recorded as AEs. Investigators used their judgement regarding reporting of additional PE findings as AEs.

Clinical laboratory results marked as clinically significant by the Investigator were captured as AEs.

AE's with start dates prior to the first IP administration will be included in the listings, but not in the summaries.

Treatment-emergent AEs (TEAE) are AEs with start dates between administration of the first IP and last IP administration + 30 days. However, if an AE is related to IP then there is no upper bound on the start date. Thus, treatment related TEAEs may have start dates beyond 30 days post IP administration.

All AEs will be coded based on MedDRA (V20.0).

Where provided in Protocol Appendix 1, AEs will be graded according to the Vital Sign and Systemic Toxicity Assessments.

N (%) of subjects with at least one TEAE and N (%) of subjects with at least one treatment-related treatment-emergent AE (TRAE) will be summarized. TEAE and TRAE by worst severity will be summarized. Note that the protocol uses the term "vaccine associated" AEs, but the eCRF collects AEs as related, not related.

N (%) of subjects with TEAE will be reported by System Organ Class and Preferred Term (SOC/PT) and maximum severity. N (%) of subjects with TRAE will be reported by SOC/PT and maximum severity.

N (%) of subjects with TEAE by SOC/PT by overall frequency (decreasing) will be reported. N (%) of subjects with TRAE will be reported by SOC/PT by overall frequency (decreasing).

All AEs will be included in the listings. Only treatment emergent AEs will be summarized. Separate listings of subjects who died, discontinued the study due to an AE, or experienced a serious AE, if any, will be provided.

No statistical test comparing adverse event rates will be done.

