2.2. Study Endpoints

2.2.1. Primary Endpoints

The primary endpoints are:

1. The number and percentage of study participants who experience any vaccine-associated AEs or SAEs after Bris10 M2SR or placebo administration.
2. The number and percentage of study participants who experience any vaccine-associated AEs or SAEs after Sing2016 M2SR or placebo administration.

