6.2.1.6. Symptom Memory Aids

Subjects will be asked to record post-treatment symptoms in a Symptom Memory Aid ([Appendix 5](#)) at the time points specified in the Schedule of Events ([Table 3](#)) for reactogenicity. At time of first dose, the first entries will be in concert with study staff as a training session at pre-dose, the second entry will be the evening of vaccination and subsequent 6 entries will be made each evening following the IP delivery. Since visit Day 36 may occur ± 1 day, the subject may not complete all days listed on the memory aid prior to the first post-dose visit. For subjects who attend the clinic at Day 35, a stamped and pre-addressed envelope will be provided so that the diary may be completed and mailed to the Site. Symptoms recorded on diaries returned by mail will be reviewed with the subject by telephone, if needed. Subject diaries will be retained as source documents.

Events that are reported in the Symptom Memory Aid will be reviewed by the study staff and assessed and recorded as AEs according to the appropriate toxicity scale ([Appendix 1](#) for vital signs and systemic AEs and [Appendix 3](#) for reactogenicity assessments). During this time, subjects are asked to take their oral temperature (at approximately the same time each evening using the thermometer provided to them by the site) and record it in the Symptom Memory Aid. Any medications taken by the subjects will also be recorded in the Symptom Memory Aid. In addition,

subjects will be asked to record symptoms they may be experiencing during this time period, including:

- Feverish
- Nasal irritation
- Nasal bleeding
- Runny nose
- Stuffy nose/Congestion
- Sore/scratchy/itchy or painful throat
- Body/muscle aches
- Joint pain
- Headache
- Cough
- Body rash
- Tiredness
- Nausea
- Vomiting
- Other symptoms

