9.4. Reactogenicity

Reactogenicity events may be common and are known to occur for the vaccine being studied and will be collected as solicited AEs in a standard, systematic format using a grading scale based on functional assessment or magnitude of reaction. In this study, the following reactogenicity events will be collected for the first 7 days after each dose of IP:

- Feverish
- Nasal irritation
- Nasal bleeding
- Runny nose
- Stuffy nose/Congestion
- Sore/scratchy/itchy or painful throat
- Body/muscle aches
- Joint pain
- Headache
- Cough
- Body rash
- Tiredness
- Nausea
- Vomiting
- Other symptoms

These will be evaluated and graded daily based on the functional scale specified within the Symptom Memory Aid ([Appendix 5](#)).

Should a subject experience a severe reaction (graded as a 3) and/or measure a body temperature equal to or greater than 39°C, he/she should immediately contact the site.

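### Diary symptoms reach the primary AE percentage only if investigators entered them as AEs and judged them related; with no reconciliation, any under-count cannot be sized

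*SAP*

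**What the plan says.** Protocol 2.2.1 sets one primary endpoint per vaccine. For Sing2016 it reads: "The number and percentage of study participants who experience any vaccine-associated AEs or SAEs after Sing2016 M2SR or placebo administration". The Bris10 endpoint is worded the same way.

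SAP 9.2 measures this as treatment-related treatment-emergent AEs (TRAEs). It explains that the protocol speaks of vaccine-associated "AEs, but the eCRF collects AEs as related, not related".

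On how diary entries become AEs, the documents give these statements:

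- Protocol 6.2.1.6: "Events that are reported in the Symptom Memory Aid will be reviewed by the study staff and assessed and recorded as AEs".
- Protocol 9.4, on reactogenicity events in the first 7 days after each dose: they "will be collected as solicited AEs in a standard, systematic format using a grading scale based on functional assessment or magnitude of reaction".
- SAP 9.2: "A symptom recorded by the subject on the Symptom Memory Aid (SMA) may or may not have been reported as a solicited AE".
- SAP 9.2, on checking: "There was no reconciliation of the database between the SMA symptoms and adverse event reports".

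SAP 9.2 adds that investigators worked from a written guideline dated 16 October 2019, and that they were told to record individual symptoms as AEs so that no reactogenicity event would be missed.

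SAP 9.2.1 tabulates the diary separately: each symptom by worst severity, number of days and timepoint, for each dose and treatment. These tables use the Evaluable Set (EVAL), which SAP 2.1.1.3 limits to subjects who received both doses. The rest of SAP 9 is headed as a Safety Set evaluation.

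**The concern.** For an intranasal vaccine in healthy adults, solicited nasal and systemic symptoms in the week after dosing can be expected to form a large part of the vaccine-associated AEs. A diary symptom with no AE record has no causality entry and cannot appear in the TRAE tables, whatever its severity.

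SAP 9.2 gives two accounts that do not fit together. In one, symptoms were recorded so that capture was complete. In the other, a symptom "may or may not have been reported as a solicited AE" and nobody compared the two data sources. A reader of the primary percentage cannot tell which account describes it.

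At stake is the absolute rate. The trial reports tolerability as percentages per arm, with no test of AE rates. If capture is incomplete, each percentage and each difference from placebo is too low, and nothing planned would show by how much.

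**Working it through.** **1. The plan's own figure.** The sample size has no rate, effect size or power behind it (SAP 11), so only its arithmetic can be reproduced: 5 × 50 = 250, that is 200 active and 50 placebo, in agreement with SAP 1.1.1. Actual enrolment was about 40 per group (SAP 12). The documents give no AE rate and no diary-to-AE conversion rate, so every rate below is an assumption.

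**2. Effect on a subject-level rate.** Let p be the proportion of subjects with a diary reaction that would count as vaccine-associated if every entry were converted. Let c be the proportion of those subjects with at least one such reaction entered and judged related. Observed rate = c × p. Take p = 60% on vaccine and 40% on placebo:

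| c | Vaccine | Placebo | Difference | Ratio |
|---|---|---|---|---|
| 1 | 60% | 40% | 20 points | 1.5 |
| 0.75 | 45% | 30% | 15 points | 1.5 |
| 0.5 | 30% | 20% | 10 points | 1.5 |
| 0.25 | 15% | 10% | 5 points | 1.5 |

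**3. Symptom-level conversion is not c.** The endpoint counts a subject once for any related AE, so one converted symptom is enough. If a subject has k symptoms, each converted independently with probability s, then c = 1 − (1 − s)^k. With k = 3:

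- s = 0.6: c = 1 − 0.4³ = 0.936, giving 56.2% vs 37.4%, a difference of 18.7 points.
- s = 0.4: c = 1 − 0.6³ = 0.784, giving 47.0% vs 31.4%, a difference of 15.7 points.

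If an investigator tends to enter all of a subject's symptoms or none, c = s. The differences are then 0.6 × 20 = 12 points and 0.4 × 20 = 8 points. The loss depends strongly on clustering, which the documents do not describe.

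**4. Variation between sites.** Suppose four equal sites with c = 0.9, 0.7, 0.5 and 0.3. Vaccine rates would be 54, 42, 30 and 18%, and placebo rates 36, 28, 20 and 12%. Pooled, that is 36% vs 24% instead of 60% vs 40%. The ratio is still 1.5, because arms are balanced within site (SAP 1.1.2.1).

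**5. Against sampling error.** With 40 per arm, 24/40 (60%) has an exact 95% interval of 43 to 75%, and 12/40 (30%) has 17 to 47%. The half-width is about 15 to 16 points. A subject-level c of 0.5 moves the vaccine rate by 30 points, well beyond that. The k = 3, s = 0.6 case moves it by 60 − 56.2 = 3.8 points, well within it.

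**6. Do the diary tables recover the count?** The primary evaluation needs subjects with any event, on the Safety Set. SAP 9.2.1 gives each symptom separately, and one subject can appear under several, so an any-symptom count cannot be rebuilt from the tables. It also uses EVAL, so a subject who stopped after dose 1, for a reaction or any other reason, drops out even of the dose 1 tables.

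**The case against.** The strongest reply is that the protocol never required one AE per diary entry. Protocol 6.2.3 has solicited symptoms reported after investigator review, either separately or combined under one term, and Protocol 9.6 prefers a diagnosis where symptoms share a cause. A symptom with no AE of its own may sit inside a combined term, or may properly have been judged not to be an AE. A common guideline was in use, assessors were blinded (Protocol 5.6), and diary symptoms are tabulated whether or not an AE was entered.

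Much of this stands, and it rules out several stronger readings that a reader might infer:

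- *That AEs were in fact under-counted.* No passage reports an omission. Missing reconciliation means omission cannot be checked; it does not show that omission occurred.
- *That the shortfall varied by site.* This is plausible where local investigators judge, but no passage reports it. The guideline's content is not in the documents, so the discretion it left is unknown.
- *That the comparison of arms is biased.* Within-site randomization and blinded assessment largely protect the ratio if c is unrelated to arm. That protection is not exact: by step 3, c would rise if vaccine recipients report more symptoms each.
- *That sentinel subjects were assessed before the guideline existed.* The guideline is dated after the August 2019 initiation in the synopsis, but no first-dose date is given.

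The reply does not remove the gap. Protocol 9.3 says that doubtful observations should be reported, and it reserves the not-related label for events with evidence of another explanation. An unentered symptom never receives that assessment on record. Protecting the ratio does not protect an endpoint that is an absolute percentage.

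**Conclusion.** The point holds as a limit on interpretation that can be repaired. The primary percentage is an investigator-assessed rate. For diary symptoms it rests on an unreconciled entry step, which SAP 9.2 describes in two incompatible ways and which sits uneasily with Protocol 6.2.1.6 and 9.4. Absolute vaccine-associated AE rates and risk differences may be too low by an amount the plan cannot size.

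Under the assumed 60% vs 40%, the 20-point difference could fall to anywhere between 18.7 and 5 points over the values tried. The upper end assumes several independently converted symptoms per subject; the lower end assumes that only a quarter of affected subjects are captured. The between-arm ratio is largely protected if conversion is unrelated to arm. The SAP's grouping of symptoms as upper respiratory infection does not alter this, because it covers only unrelated AEs and is a secondary presentation.

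**What to change.** In SAP 9.2:

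1. Describe the primary TRAE count as investigator-assessed, and reconcile the two statements about capture of diary symptoms.
2. Beside it, on the Safety Set and labelled as a sensitivity presentation, report N (%) of subjects per arm and dose with any diary-derived solicited reaction, by worst severity. Define a reaction as any listed symptom scored 1 or more from the post-dose Day 1 entry to Day 7 and above the pre-dose entry where one exists, or a measured oral temperature in the Appendix 1 fever range. Do not merge this count with related AEs, since symptoms without a causality entry are not thereby related.
3. Cross-tabulate diary symptoms against AE entries by arm and site, counting a symptom as matched when a combined term covers it.
4. Before lock, list diary scores of 3 with no matching AE and query the site.

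In SAP 9.2.1, run the diary tables on the Safety Set, with the dose 2 tables restricted to those who received dose 2.

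The cost is SAP wording, a derived variable, a few tables and one round of site queries. The tables need no new data; the queries need site time and must come before lock. The diary-derived percentage will be higher and less favourable, and it will include background symptoms, which the placebo arm shows.

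### SAP 9.2 gives two URI grouping rules that disagree: the 15-term rule fails the SAP's own example, requires no respiratory symptom, and the display omits investigator-reported URTIs

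*SAP*

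**What the plan says.** SAP Section 9.2 introduces the grouping after a medical review of the AE listing. The motivating case is that "a subject who reported concurrent cough, runny nose, and sneezing assessed by the investigator as unrelated to vaccine should have those symptoms grouped" as a URI. The narrative rule follows: "as a secondary presentation, subjects with 3 or more concurrent unrelated AEs of cough, runny nose/rhinorrhea, sneezing, sore throat, itchy throat, itchy eyes", continuing with "congestion, nasal irritation, hoarseness, headache, body aches/myalgia, tiredness/fatigue, malaise, and fever will have those AEs grouped as URI".

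The next paragraph turns that standard into coding terms. It uses "a total of 15 different AE Preferred Terms". The first nine are "Arthralgia, Cough, Fatigue, Headache, Malaise, Myalgia, Nasal congestion, Nasal discomfort, Nasopharyngitis"; the other six are Throat irritation, Oropharyngeal pain, Rhinorrhea, Sinus congestion, Paranasal sinus discomfort and Pyrexia. The qualifying condition is "Subjects who reported symptoms that resulted in coding of 3 or more of these PTs on a given day", restricted to AEs the investigator judged unrelated. Finally, "AEs already reported by the Investigator as a URTI were not included in the URI data display".

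The SAP presents the grouping as consistent with the protocol. Protocol Section 9.6 asks for a diagnosis in place of separate symptoms when they share an etiology. Its illustration is five respiratory symptoms: sore throat, cough, head congestion, sneezing and runny nose.

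**The concern.** The operational rule is offered as the implementation of the narrative rule, yet the two select different subjects. Two programmers could each follow Section 9.2 and produce different tables, and the one who uses the PT list would leave ungrouped the case that the SAP says must be grouped.

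Two further features affect what the display means. Nothing requires a respiratory term, so headache, fatigue and myalgia on the same day become an upper respiratory infection. That does not fit a grouping justified by common etiology. And a display headed URI that leaves out the cases investigators diagnosed as URTI invites a reader to take a partial count for the incidence. The SAP says the grouping is meant to simplify presentation, so readers may well rely on it.

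**Working it through.** **Inputs.** Both term lists, the three-term threshold and the URTI exclusion are from SAP 9.2. The five-symptom illustration is from Protocol 9.6. The systemic grading table is in Protocol Appendix 1. About 40 subjects per arm (50 planned) is from SAP Section 12.

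**Step 1: count the terms.** The operational list contains 15 PTs, as the SAP states. The narrative list contains 14 symptoms.

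**Step 2: match the lists.** The matching is by plain meaning; the SAP gives no mapping.

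| Narrative symptom | Listed PT |
|---|---|
| cough | Cough |
| runny nose | Rhinorrhea |
| sneezing | none |
| sore throat | Oropharyngeal pain |
| itchy throat | Throat irritation |
| itchy eyes | none |
| congestion | Nasal congestion, Sinus congestion |
| nasal irritation | Nasal discomfort |
| hoarseness | none |
| headache | Headache |
| body aches | Myalgia |
| tiredness | Fatigue |
| malaise | Malaise |
| fever | Pyrexia |
| none | Arthralgia, Nasopharyngitis, Paranasal sinus discomfort |

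Three narrative symptoms have no PT, and three PTs have no narrative symptom.

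**Step 3: apply the operational rule to the SAP's example.** Cough (1) + Rhinorrhea (1) + sneezing (0) = 2, which is below 3, so the case is not grouped. If sneezing were coded to Rhinorrhea, the number of distinct PTs would still be 2.

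**Step 4: apply it to the Protocol 9.6 illustration.** All five symptoms together give 4 listed PTs, which qualifies. Of the C(5,3) = 10 three-symptom subsets, C(4,2) = 6 contain sneezing. Each of those scores 2 and fails.

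**Step 5: count combinations with no respiratory term.** Six PTs are systemic: Arthralgia, Fatigue, Headache, Malaise, Myalgia and Pyrexia.

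- Operational list: C(6,3) = 20 of C(15,3) = 455, or 20/455 = 4.4%.
- Narrative list (headache, body aches, tiredness, malaise and fever are systemic): C(5,3) = 10 of C(14,3) = 364.

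These are shares of possible combinations, not of subjects. Both versions of the rule have the gap.

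**Step 6: weight of one omitted URTI.** For a subject with an investigator-reported URTI who is not otherwise captured, the displayed proportion falls by 1/40 = 2.5 percentage points, or 1/50 = 2.0 at the planned size. The documents give no counts. For an assumed 1, 2 or 4 such subjects in an arm of 40, the shortfall is 2.5, 5 or 10 points.

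**The case against.** The strongest reply is that little depends on this display. It is labelled secondary, no AE rates are tested, and only AEs already judged unrelated enter it. All of that stands, and it rules out several stronger readings:

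- **That the primary endpoint is affected.** The primary endpoint is vaccine-associated AEs or SAEs, and SAP 9.2 analyses vaccine association as relatedness to IP. Regrouping unrelated AEs cannot change a related-AE count. It also leaves unchanged the number of subjects with at least one treatment-emergent AE, since a grouped subject still has one.
- **That reactogenicity is converted into unrelated infection.** The causality judgement comes first and the grouping does not alter it. An AE judged related never enters the rule.
- **That component symptoms disappear.** SAP 9.2 separately requires treatment-emergent AEs by SOC and PT, with all AEs listed, and SAP 9.2.1 tabulates the named memory aid symptoms from the subjects' own entries. Nothing says component terms are removed from those tables.
- **That the grouping is undisclosed as post hoc.** Section 9.2 says it followed a review of the AE listing.

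It can also be said that the missing sneezing term may change nothing if no such AE was coded, that the narrative list itself includes systemic symptoms, and that the URTI exclusion is stated openly. The first is possible but cannot be settled from the documents. The second shows that systemic terms were meant to contribute; it does not justify a URI made up only of them, given Protocol 9.6. The third makes the omission a labelling problem rather than a hidden one, and treatment-emergent investigator URTIs still appear in the SOC and PT tables. None of this removes the contradiction between the two rules.

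**Conclusion.** The point holds as a specification error in one secondary presentation. Followed literally, the operational rule contradicts the standard it claims to implement (2 of the 3 terms needed in the SAP's own example) and admits 20 of 455 three-term combinations with no respiratory symptom. Because the display also omits investigator-reported URTIs, it is not a measure of URI incidence.

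A reader might infer that the URI rates by arm will be wrong. The documents do not support that. The SAP neither calls the display a total URI rate nor says it is shown by arm. The possible errors run in both directions: missing terms and excluded URTIs lower the count, and purely systemic triads raise it. With no event counts, neither size nor direction can be given.

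The verdict assumes that sneezing does not code to a third, distinct listed PT, and that the six named PTs are systemic. Appendix 1 grades headache, fatigue and myalgia as systemic and fever under vital signs; placing Arthralgia and Malaise with them is a reading.

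**What to change.** 1. Replace the two lists with one list of PTs that covers sneezing, itchy eyes and hoarseness. State whether the three PTs without a narrative counterpart stay, and confirm that the worked example qualifies.
2. Require at least one respiratory PT among the three, and name in the SAP which PTs count as respiratory.
3. Show three rows: subjects with derived URI, subjects with investigator-reported URTI, and subjects with either. Label the display to match. State whether Nasopharyngitis counts as a URTI for the exclusion, which the SAP leaves open.

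A split at 7 days after each dose and a note in SAP Section 12 are optional. The cost is SAP wording and reprogramming of one secondary table, with no new data. Purely systemic triads would leave the URI display, but their component AEs remain in the SOC and PT tables.

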9. ADVERSE EVENT REPORTING

9.1. Definitions

Adverse Event

An AE is any untoward medical occurrence in a clinical study subject administered a medicinal (investigational or non-investigational) product. An AE does not necessarily have a causal relationship with the treatment. An AE can therefore be any unfavorable and unintended sign (including an abnormal finding), symptom, or disease temporally associated with the use of a medicinal (investigational or non-investigational) product, whether or not related to that medicinal (investigational or non-investigational) product.

This includes any occurrence that is new in onset or aggravated in severity or frequency from the baseline condition, or abnormal result of diagnostic procedures, including clinical laboratory test abnormalities.

AEs will be monitored continuously from the first administration of IP treatment until Day 57. SAEs or medically attended events will be documented until Day 209. Events recorded at the follow-up phone call will be assessed and followed up as appropriate.

Serious Adverse Event

An SAE is any untoward medical occurrence that meets any of the following conditions:

- results in death;
- is life-threatening, i.e., the subject was at risk of death at the time of the event (e.g., ventricular fibrillation and anaphylaxis). The term does not refer to an event which hypothetically might have caused death if it were more severe.
- requires inpatient hospitalization or prolongation of existing inpatient hospitalization:
 - Hospitalization refers to an overnight admission into hospital for the purpose of investigating and/or treating the AE. Hospitalization for an elective procedure, or routinely scheduled treatment for a pre-existing condition that has not worsened, is not an SAE.
- results in persistent or significant disability/incapacity, i.e., causing substantial disruption of the subject's ability to conduct normal life;
- is a congenital anomaly/birth defect;
- is medically significant, i.e., may not be immediately life-threatening or result in death or hospitalization but may jeopardize the subject's health or may require intervention to prevent one of the above outcomes. Examples of such events are intensive treatment in an emergency room or at home for allergic bronchospasm, blood dyscrasias, or convulsions that do not result in hospitalization or development of drug dependency or drug abuse.

Unlisted (Unexpected) Adverse Event

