9.2. Intensity of Adverse Events

All AEs will be assessed by the clinician using the grading system from FDA vaccine toxicity criteria ([Appendix 1](#) for vital signs and systemic AE assessment; [Appendix 2](#) for laboratory AE assessment, and as described in Section 6.2.2). For assessment of reactogenicity in this study, see [Appendix 3](#). For events not included in the protocol-defined grading system, then the following guidelines will be used to quantify intensity.

Mild: events require minimal or no treatment and do not interfere with the patient's daily activities.

Moderate: events result in a low level of inconvenience or concern with the therapeutic measures. Moderate events may cause some interference with functioning.

Severe: events interrupt a patient's usual daily activity and may require systemic drug therapy or other treatment. Severe events are usually incapacitating.

Life threatening: any adverse drug experience that places the patient or subject, in the view of the investigator, at immediate risk of death from the reaction as it occurred, i.e., it does not include a reaction that had it occurred in a more severe form, might have caused death.

Changes in the severity of an AE should be documented to allow an assessment of the duration of the event at each level of intensity to be performed. Adverse events characterized as intermittent require documentation of onset and duration of each episode.

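### The SAP's treatment-emergent definition has no worsening clause, so an AE kept under a pre-dose start date is left out of every TEAE and TRAE table even if it worsens after vaccination

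*SAP*

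**What the plan says.** **Protocol.** Section 9.1 gives the AE definition two limbs: "This includes any occurrence that is new in onset or aggravated in severity or frequency from the baseline condition". Section 9.2 adds: "Changes in the severity of an AE should be documented to allow an assessment of the duration of the event at each level of intensity". It does not say whether a worsening opens a new AE record with its own start date or stays on the existing one. The primary endpoint for Bris10 in section 2.2.1 is: "The number and percentage of study participants who experience any vaccine-associated AEs or SAEs after Bris10 M2SR or placebo administration". A parallel endpoint covers Sing2016.

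**SAP section 9.2.** The definition is: "Treatment-emergent AEs (TEAE) are AEs with start dates between administration of the first IP and last IP administration + 30 days". One exception follows: "However, if an AE is related to IP then there is no upper bound on the start date". For events with earlier onset: "AE's with start dates prior to the first IP administration will be included in the listings, but not in the summaries". The scope of the tables is then fixed: "Only treatment emergent AEs will be summarized". The SAP notes that the protocol's vaccine-associated events are those marked related on the eCRF, so the TRAE tables carry the primary endpoint.

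**Start of AE capture.** SAP 9.2 says: "Adverse events were to be recorded from informed consent". Protocol 9.1 and 6.2.3 start general AE monitoring at first IP administration. For the screening period, which may begin 30 days before dosing, protocol 6.1.1 asks only for SAEs and medically attended AEs.

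**The concern.** The protocol's second limb, aggravation, has no counterpart in the analysis rule. Relatedness does not restore it: a related event is freed from the upper date limit but not from the lower one. Suppose a mild complaint is recorded during screening, becomes severe after vaccination and stays on one record. It then appears only in the listings, whatever the investigator thinks of the worsening.

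This matters because safety is the primary objective, the study is the first in humans for Sing2016, and AE rates are not tested. The descriptive counts are therefore the result. For any affected subject the rule works in one direction: it removes the subject from a count or lowers the worst severity shown.

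**Working it through.** The plan has no figure to reproduce here. The 50 per group was chosen empirically, with no assumed event rate. The check is a trace of the rules, followed by a scale for one subject.

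**Trace: which worsened events reach the AE tables?**

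1. *AE recorded once, start date before first IP, worse after dosing.* It fails the lower bound and is excluded from all TEAE and TRAE tables. If judged related it is still excluded, because only the upper bound is lifted.
2. *Baseline condition whose aggravation is entered as an AE dated at the worsening.* The start date falls after first IP, so it is included.
3. *AE that starts after dose 1 and worsens after dose 2.* It is included, at worst severity.
4. *Worsening of a diary symptom, laboratory value or vital sign.* It is still visible in the Symptom Memory Aid worst-severity tables (SAP 9.2.1), the maximum laboratory shift (SAP 9.3) or the vital-sign change from baseline (SAP 9.4). None of these filters on AE start date.

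Only case 1 loses the event. What separates it from case 2 is a recording convention that neither document states.

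**Can case 1 arise?** Yes. The SAP itself provides a rule for AEs that start before dosing. Even under the narrower protocol rule, medically attended AEs are recorded from screening. The reference in protocol 9.2 to the length of an event at each intensity fits a single continuing record, though it does not require one.

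**Scale.** Effect on an arm's percentage = 100 × k / n, where k is the number of affected subjects with no other event that would put them in the same table.

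- n = 40 (SAP section 12, approximate actual enrolment), k = 1: 100 × 1/40 = 2.5 points.
- n = 50 (planned), k = 1: 100 × 1/50 = 2.0 points.

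The documents give no value for k. Assuming 0 to 3 for illustration, and no other counted events in the arm, the exact (Clopper-Pearson) 95% intervals at n = 40 are:

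| Subjects with event | Percentage | 95% interval |
|---|---|---|
| 0/40 | 0 | 0 to 8.8 |
| 1/40 | 2.5 | 0.1 to 13.2 |
| 2/40 | 5.0 | 0.6 to 16.9 |
| 3/40 | 7.5 | 1.6 to 20.4 |

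The intervals overlap heavily, so one or two missed subjects would hardly change an estimate of a common event. The practical difference is whether a rare, severe or related event appears in the table at all.

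**The case against.** Three stronger readings are tempting, and the documents support none of them.

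- *That worsened events vanish from every primary safety table.* They do not. The diary, laboratory and vital-sign summaries also belong to SAP section 9 and are untouched. All AEs are listed, with separate listings for SAEs and for discontinuations due to an AE.
- *That the loss is certain.* Protocol 9.1 makes the aggravation itself an AE. A site that enters it so gives it a post-dose start date, and it counts.
- *That related worsening would routinely be missed from the primary endpoint.* Under protocol 9.3, an event that precedes exposure is ordinarily rated not related. An investigator who thinks the vaccine made something worse may well open a new record.

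The pool is also likely to be small. Protocol 6.1.1 collects few AE types before dosing, clinically significant screening findings exclude the subject, and exclusion 25 delays vaccination for acute illness and enrols minor illness only after it resolves. A subject with any other TEAE stays in the overall TEAE count.

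All of this limits the size of the problem but does not remove it. The other summaries do not replace the lost count, since none carries relatedness and none yields the primary endpoint. The diary tables use only subjects who received both doses, cover 7 days after each, leave other symptoms to listings and were not reconciled with the AE data. A subject whose pre-dose AE worsened and who never received dose 2 could be absent from both the diary tables and the TEAE tables. The argument from site practice rests on a convention that neither document states.

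**Conclusion.** The mismatch is real and is a stated rule, not missing detail. The protocol counts aggravation as an AE; the SAP admits an event to the TEAE and TRAE tables only if its recorded start date is not before first IP. An AE kept under its pre-dose start date is excluded from those tables even if it worsens after vaccination.

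The conclusion on actual loss is conditional on worsening being kept on the original record. The number affected is unknown and may be zero. At about 40 per arm, each affected subject with no other TEAE is worth 2.5 points in the overall TEAE percentage; with another TEAE, the effect is confined to the term-level and worst-severity rows. The direction is fixed: AE counts or worst severity can only be understated. Nothing in the documents shows that the loss would differ between arms.

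**What to change.** In SAP 9.2:

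- Define a TEAE as an AE that starts on or after first IP administration, or that starts before it and worsens in severity or frequency after it.
- Date emergence at the worsening, apply the existing window to that date, and report the post-dose severity.
- Apply the same rule to TRAEs, using the investigator's relatedness assessment for the worsening. Do not admit a pre-dose AE merely because it is marked related. Without worsening, that would bring in events that began before exposure, against protocol 9.3.
- State whether a worsening is a new eCRF record or is derived from severity changes on the existing one. If dated severity changes are not in the database, identify these cases by a review of the listed pre-dose AEs, done blind to treatment.
- Reconcile protocol 6.1.1, 6.2.3 and 9.1 with SAP 9.2 on when AE capture starts.

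The cost is a short change to the SAP text and, depending on how severity changes were stored, either a programming condition or a brief listing review. Protocol 9.2 already requires severity changes to be documented, but no data source for frequency is described, so that part may need the review. AE percentages may rise slightly.
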